11 STATISTICAL EVALUATION

11.1 Determination of Sample Size

Assuming placebo participants would experience 1.43 episodes of URTIs and 7.42 duration days of URTI symptoms during 84 days of follow up (22), a sample size of 100 participants (50 participants per arm) has a power of 80% to detect a rate of \leq 0.76 for the number of episodes of URTIs and \leq 5.80 for the duration days of URTI symptoms in the Bacillus coagulans SNZ 1969 group using Poisson regression model.

In addition, a sample size of 100 participants could detect an effect size ≥ 0.63 in the AUC of GITI symptom scores and in the AUC of the Additional Respiratory Tract Symptoms questionnaire, and a difference of ≥27.8 score.day in the mean of AUC of CARIFS daily total symptom scores between Bacillus coagulans SNZ 1969 and placebo groups assuming standard deviations equal to 52.96 and 32.85 score.day for Bacillus coagulans SNZ 1969 and placebo groups (22), respectively, using two-sample t-test with 80% power, 2-sided 5% significance level, and 20% dropout rate.

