11.3 Statistical Analysis Plan

For both count and continuous primary and secondary outcomes, summary statistics including number of participants, mean, median, standard deviation, first quartile, third quartile, minimum, and maximum will be obtained for each available time interval and for each group. For categorical outcomes, frequencies and percentages will be presented.

The difference in the number of incidences of URTI, duration days of URTI, missed school days, well days, illness days between Bacillus coagulans SNZ 1969 and Placebo groups will be assessed by computing the rate ratio with 95% confidence interval using a generalized linear model with log link function (Poisson or negative binomial regression model).

The difference in the number of incidences of Additional Respiratory Symptoms and the duration days of Additional Respiratory Symptoms between Bacillus coagulans SNZ 1969 and Placebo groups will be assessed by computing the rate ratio with 95% confidence interval using a generalized linear model with log link function (Poisson or negative binomial regression model).

The difference in the number of incidences of GITI symptoms, duration days of GITI symptoms, missed school days, well days, illness days between Bacillus coagulans SNZ 1969 and Placebo groups will be assessed by computing the rate ratio with 95% confidence interval using a generalized linear model with log link function (Poisson or negative binomial regression model).

The difference in the AUC for daily total CARIFS scores, the mean total severity scores of URTI symptoms, the AUC for daily total Additional Respiratory Tract Symptoms questionnaire scores, the AUC of GITI symptom scores, and mean of GITI symptom scores between Bacillus coagulans SNZ 1969 and Placebo groups will be assessed by two-sample t-test if the outcome is normally distributed and Wilcoxon's rank sum test if the outcome is not normally distributed. Normality assumption will be assessed using quantile-quantile (Q-Q) plots.

Fisher's exact test will be used to assess the difference of proportion of participants who used prescription and non-prescription cold/flu medications to treat URTI/GITI symptoms between Bacillus coagulans SNZ 1969 and Placebo. 95% confidence interval of odds ratio will be calculated.

Differences between groups for sIgA, IgA, IgG, IgE, IgM, and immune response biomarkers at day 84 will be assessed by ANCOVA model adjusting for baseline values.

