To assess the goodness of fit of the log link models, the Poisson regression model and the negative binomial regression model will be applied to the same dataset and then the Likelihood Ratio Test will be performed. If the p-value of the test is less than 0.05, then we will use the negative binomial model as it offers a better fit of the count data.

To evaluate the adequacy of ANCOVA model, diagnostics including Q-Q plots (for assessing the normality of error terms) and plots of residuals versus fitted values (to examine if the residuals are independent and have constant variance) will be generated. If these diagnostic plots indicate deviations from the model's assumptions, ranks or other transformation of the dependent variable, will be implemented.

Two-sided probabilities ≤ 0.05 will be considered statistically significant. All statistical analysis will be completed using the R Statistical Software Package Version 4.3.2 or newer for Microsoft Windows.

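### Choosing Poisson or negative binomial by a likelihood ratio test, with no robust variance on offer, can miscalibrate the intervals for URTI duration days and, modestly, for URTI episodes

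*Protocol*

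**What the plan says.** Section 11.3 analyses the counts of URTI episodes, and "duration days of URTI, missed school days, well days, illness days between Bacillus coagulans SNZ 1969 and Placebo groups", by a rate ratio "using a generalized linear model with log link function (Poisson or negative binomial regression model"). It then fixes how to choose: "the Poisson regression model and the negative binomial regression model will be applied to the same dataset and then the Likelihood Ratio Test" is performed, and negative binomial is used if p is below 0.05. No robust, quasi-likelihood or permutation alternative is named for these outcomes.

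Section 11.1 gives the planning values: "Assuming placebo participants would experience 1.43 episodes of URTIs and 7.42 duration days of URTI symptoms during 84 days of follow up". It claims that "a sample size of 100 participants (50 participants per arm) has a power of 80% to detect a rate of" 0.76 episodes or fewer, and "5.80 for the duration days of URTI symptoms in the Bacillus coagulans SNZ 1969 group using Poisson regression model".

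Section 9.7.7 requires at least two consecutive symptomatic days for a CARIFS episode. It defines duration for each episode, from onset to the last symptomatic day before two days at zero. It does not say how several episodes in one child are combined. Section 5 lists URTI incidence and duration among the primary outcomes.

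**The concern.** The rule lets the trial data pick the variance model and restricts the pick to two. With group as the only covariate and equal follow-up, both models estimate the same ratio of means. Only the standard error differs, so the rule decides the width of the interval and nothing else.

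Two features make that width unreliable. First, symptom days come in runs, with a spike of children at zero. Neither a Poisson nor a negative binomial distribution has that shape. Second, a pretest with little power to see mild overdispersion will often leave Poisson in place when its standard error is too small. What is at stake is the coverage of the intervals for URTI incidence and URTI duration, and part of the already limited power for duration.

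**Working it through.** **Inputs.** From section 11.1: 1.43 and 0.76 episodes, 7.42 and 5.80 days, 50 per arm, two-sided 5%, 20% dropout. The dropout is stated in the t-test sentence ("using two-sample t-test with 80% power, 2-sided 5% significance level, and 20% dropout rate"). Step 1 shows that it was also applied to the counts, giving 40 per arm. The protocol gives no dispersion and no distribution of episode lengths, so those below are assumptions.

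**Step 1: the plan's own figure.** Under Poisson, SE(log rate ratio) = sqrt(1/(n·m1) + 1/(n·m2)).
- Episodes, n = 40: SE = sqrt(1/57.2 + 1/30.4) = 0.224; ln(1.43/0.76) = 0.632; z = 2.82; power = Φ(2.82 − 1.96) = 80.4%.
- Days, n = 40: SE = sqrt(1/296.8 + 1/232) = 0.0876; ln(7.42/5.80) = 0.246; z = 2.81; power = 80.3%.
- With n = 50 both come to 88%.

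The stated 80% is reproduced, with variance equal to the mean.

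**Step 2: what summed days look like.** Mean episode length is 7.42/1.43 = 5.19 days. If episodes are Poisson, the share of placebo children with none is exp(−1.43) = 24%. For a sum of Poisson episodes, Var = 1.43·(length variance + 5.19²). Two assumed length distributions, both with a minimum of 2 days:
- Low variance (2 + Poisson): length variance 3.19; Var = 1.43 × 30.1 = 43.1; variance/mean = 5.8; true null SE = sqrt(2 × 43.1/(40 × 7.42²)) = 0.198.
- Geometric (2 + geometric): length variance 3.19 × 4.19 = 13.4; Var = 1.43 × 40.3 = 57.6; variance/mean = 7.8; true null SE = 0.229.

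**Step 3: why negative binomial overshoots.** Matching these variances needs dispersion (Var − mean)/mean² = 0.65 and 0.91. Matching 24% zeros at mean 7.42 needs about 1.9, since (1 + 1.9 × 7.42)^(−1/1.9) = 0.24. Maximum likelihood settles in between, at about 1.11 and 1.30 in simulation. The negative binomial SE is sqrt(2(1/7.42 + dispersion)/40) = 0.249 and 0.268, above the true values.

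**Step 4: simulating the rule for days** (40 per arm; power at 5.80 days with fewer episodes on active). In all five scenarios the test chose negative binomial in essentially 100% of trials.

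| Assumed days | True SD of log ratio (null) | Negative binomial SE (null) | Type I error, rule | Power, rule | Power, robust |
|---|---|---|---|---|---|
| Sum, low-variance lengths | 0.20 | 0.249 | 1.3-1.8% | 9% | 22% |
| Sum, geometric lengths | 0.229 | 0.269 | 2.8% | 10% | 18% |
| Sum, lognormal lengths | 0.257 | 0.273 | 4.2% | 12% | 17.5% |
| True negative binomial, dispersion 1 | 0.239 | 0.235 | 6.2% | 18% | 18% |
| Per episode, ill children only, geometric | 0.204 | 0.179 | 9.1% | not comparable | not comparable |

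A hand check of the geometric row: null rejection is about 2Φ(−1.96 × 0.269/0.229) = 2.1%, close to the simulated 2.8%. A further simulation of summed days gave type I error 1.5-2.8% and power 6-11%, against 4.6-6.2% and 15-21% with robust variance. If the benefit comes through shorter rather than fewer episodes, power is 13% under the rule against 19-25% robust.

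**Step 5: simulating the rule for episodes** (null, mean 1.43, 40 per arm).
- At dispersion 0.1, 0.15, 0.2 and 0.3, negative binomial is chosen in 10%, 18%, 30% and 52% of trials.
- Type I error of the rule is 6.3%, 6.6%, 7.6% and 6.3%. A further run at 0.1-0.3 gave 5.7-6.7%, against 5.0-5.4% with robust variance.
- When the data are truly Poisson, the nominal 5% test rejects in only 1.3-1.6% of trials, because zero dispersion lies on the boundary of the parameter space.

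**The case against.** **The selection test is not at fault for days.** This stands. The test rightly rejects Poisson, whose type I error for days would be about 40-58%. The fault there is a two-model menu without a robust variance; the pretest itself does harm only for episodes.

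**The standard-error estimator could be left to the SAP.** This stands in part. Section 11.3 does not name an estimator. But it does fix the two models and the rule for choosing, and that choice would be idle if a robust variance were used under either model.

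**The episode effect is small.** This stands. Always using negative binomial gives 5.2-6.3%, and robust or quasi-Poisson tests gave 4.8-6.6%, so part of the excess is small-sample error that any method shares. The protocol does not state the reference distribution; with the boundary-corrected p-value the rule gives 5.9-6.3%.

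**Stronger readings that the documents do not support.**
- A reader might infer that power for duration is always halved. The protocol gives no day-count distribution and no rule for combining episodes, and the table runs from a loss of more than half, through none, to an error in the other direction.
- A reader might extend the result to all three questionnaires. The Additional Respiratory and GITI measures are defined per symptom with a one-day minimum, and no rates are given for them.
- A reader might infer that well days are underdispersed, with a mean near 84 − 7.42 = 77. Section 5 also requires absence of GITI symptoms, for which no day rate is given.
- Total days of illness is a secondary outcome. The primary day count examined here is URTI duration.

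**Conclusion.** The point holds in conditional form. If URTI duration is a child-level sum of episodes lasting at least two days, following the rule yields negative binomial standard errors that are usually too wide: type I error about 1.5-4%, and power at 5.80 days about 6-12% against about 15-22% with a robust standard error. The lognormal gap is smaller than it looks, because the uncorrected sandwich test there rejected 7.0% under the null; quasi-Poisson power was 16%. For URTI episodes with dispersion of 0.1-0.3 the rule inflates type I error modestly, to about 6-7.5%.

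All of this assumes 40 children per arm, Poisson episodes for the summed days, and the stated length distributions. For summed days the error is conservative, so it costs power rather than creating false positives. Since the shape is unknown in advance, a variance estimate that does not depend on it is the safer choice. This is a cheap improvement, not a fatal flaw. It does not rescue the 80% stated for duration days: power stays near 15-30% with any valid standard error under these assumptions.

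**What to change.** In section 11.3, delete the likelihood ratio selection step. Pre-specify one analysis for the count and day outcomes: log-link Poisson regression with robust (sandwich) standard errors, reported as the rate ratio with a 95% interval. Keep negative binomial as a sensitivity analysis.

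Name a small-sample correction at the same time. Uncorrected sandwich tests are slightly liberal at 40 per arm: about 5-6% in most scenarios and about 7% for lognormal lengths. State also how a child's episodes combine into duration days, because the direction of the error depends on it.

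The cost is two sentences for the model, one for the duration definition, and a standard R package. Data collection and the meaning of the rate ratio do not change. The Poisson variance assumption behind the power statement in section 11.1 needs its own correction.

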5 STUDY OBJECTIVES

The objective of this study is to investigate the safety and efficacy of *Bacillus coagulans* SNZ 1969 on the incidence rate, duration, and severity of acute upper respiratory tract infections (URTI) and gastrointestinal tract infection (GITI) symptoms in healthy school-aged children.

Primary outcomes:

- 1. The difference in incidence, duration, and severity (area-under-the-curve (AUC)) of URTI as assessed by the Canadian Acute Respiratory Illness and Flu Scale (CARIFS) from baseline to day 84 between *Bacillus coagulans* SNZ 1969 and placebo
- 2. The difference in incidence, duration, and severity (area-under-the-curve (AUC)) of Additional Respiratory Tract Symptoms as assessed by Additional Respiratory Tract Symptoms questionnare from baseline to day 84 between *Bacillus coagulans* SNZ 1969 and placebo
- 3. The difference in incidence, duration, and severity (AUC) of GITI symptoms as assessed by the GITI Symptoms Questionnaire from baseline to day 84 between *Bacillus coagulans* SNZ 1969 and placebo

Secondary outcomes:

[figure not shown]
- 1. The difference in incidence, duration, and severity (AUC) of URTI as assessed by the CARIFS from baseline to days 28 and 56 between *B coagulans* SNZ 1969 and placebo
- 2. The difference in incidence, duration, and severity (AUC) of Additional Respiratory tract symptoms as assessed by Additional Respiratory Tract Symptoms questionnare from baseline to days 28 and 56 between *B coagulans* SNZ 1969 and placebo
- 3. The difference in incidence, duration, and severity (AUC) of GITI symptoms as assessed by the GITI Symptoms Questionnaire from baseline to days 28 and 56 between *B. coagulans* SNZ 1969 and placebo
- 4. The difference between *B. coagulans* SNZ 1969 and placebo from baseline to days 28, 56, and 84 on:
 - a. Severity of cold/flu and GITI symptoms as assessed by total and individual daily symptom scores
 - b. Number of missed school days
 - c. Number of well days, related to the absence of cold/flu and GITI symptoms
 - d. Use of prescription and non-prescription cold/flu medications to treat cold or flu symptoms
 - e. Total days of illness
- 5. The difference in change between B. coagulans SNZ 1969 and placebo from baseline to day 84 on:
 - a. Saliva secretory immunoglobulin A (sIgA) concentrations
 - b. Serum levels of Immunoglobulin A (IgA), G (IgG), E (IgE) and M (IgM)

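### The ANCOVA fallback transforms only the Day 84 value, not the baseline covariate, which wastes precision for strongly skewed markers

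*Protocol*

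**What the plan says.** Protocol section 11.3 states that sIgA, IgA, IgG, IgE, IgM and "immune response biomarkers at day 84 will be assessed by ANCOVA model adjusting for baseline values". The scale of the covariate is not stated.

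The same section then gives the remedy for poor diagnostics (Q-Q plots and residuals against fitted values): "If these diagnostic plots indicate deviations from the model's assumptions", then "ranks or other transformation of the dependent variable, will be implemented". The trigger is visual. No transformation is named, and no order is set between ranks and anything else.

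These are secondary outcomes 5a to 5c in section 5, introduced as "The difference in change between B. coagulans SNZ 1969 and placebo from baseline to day 84 on". They comprise sIgA, four serum immunoglobulins and, by count of the list, 40 array markers: 1 + 4 + 40 = 45 analyses. Section 11.1 gives no power figure for any of them.

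**The concern.** Section 11.3 commits to a remedy and says what it acts on: the dependent variable. The covariate is the same assay in the same child, so a marker skewed enough at Day 84 to fail a Q-Q plot is very probably skewed at baseline too. If the relation is linear on the log scale, a logged Day 84 value is not linear in the raw baseline. A few very large baseline values then dominate the slope, and baseline explains less of the outcome than it could.

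There is also a mismatch with the objective, which is worded as change. With both values logged, ANCOVA of the Day 84 value and ANCOVA of the change give the same treatment estimate, because the two outcomes differ only by the covariate. With a logged outcome and a raw baseline, that equivalence is lost.

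At stake is precision in the biomarker results, together with comparability: the effect scale (raw, ranked or something else) may differ from marker to marker.

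**Working it through.** **1. The plan's own sample size.** Section 11.1 gives "a sample size of 100 participants (50 participants per arm"), an effect size of 0.63 and, for CARIFS AUC, a difference of 27.8 with SDs 52.96 and 32.85, "using two-sample t-test with 80% power, 2-sided 5% significance level, and 20% dropout rate".

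- Effect size 0.63: n per arm = 2(1.96 + 0.84)²/0.63² = 39.5, so 40.
- CARIFS AUC: SD = √((52.96² + 32.85²)/2) = 44.07, and 27.8/44.07 = 0.63, so again 40.
- Dropout: 80/(1 − 0.20) = 100.

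The stated size reproduces, and 40 completers per arm is the number used below.

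**2. Assumptions.** The protocol gives no distribution for any marker. Assume a log-normal marker with log-scale SD s and correlation ρ between log baseline and log Day 84. Both are varied.

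**3. What a raw baseline keeps.** In large samples, a raw log-normal covariate keeps the share k = s²/(exp(s²) − 1) of the R² that the logged covariate would give:

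- s = 0.5: 0.25/0.284 = 0.88
- s = 1.0: 1/1.718 = 0.58
- s = 1.5: 2.25/8.488 = 0.265

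At 40 per arm, simulation (10,000 runs per setting) puts the kept share of the achievable variance reduction at 89%, 67% and 47–48%. The small-sample loss is milder than the formula suggests.

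**4. Effect on power.** Set the effect, in log-scale SD units, at 2.84·√(2/40)·√(1 − ρ²). This is 0.51 at ρ = 0.6 and 0.38 at ρ = 0.8, and gives about 80% power with both values logged. With a raw baseline the residual variance rises by the factor (1 − kρ²)/(1 − ρ²), so approximate power is Φ(2.84/√factor − 1.96).

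| s | ρ | k | Variance factor | Power, formula | Power, simulated |
|---|---|---|---|---|---|
| 0.6 | 0.6 | 0.83 | 1.10 | 77% | about 76% |
| 1.0 | 0.6 | 0.58 | 1.24 | 72% | 72–74% |
| 1.0 | 0.8 | 0.58 | 1.74 | 58% | 60% |
| 1.4 | 0.8 | 0.32 | 2.21 | 48% | 53–55% |

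The last two columns are for a logged outcome with a raw baseline at 40 per arm. Over a wider grid (ρ 0.5 to 0.85, s 0.5 to 1.5) the loss runs from about 1.5 points (ρ 0.5, s 0.5) to about 34 points (ρ 0.85, s 1.5).

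**5. Ranks.** In the last three settings of the table, a ranked outcome on a raw baseline gives 69%, 56% and 50%. Ranking both gives about 76%, 73% and 73%. So the baseline scale accounts for 7, 17 and 23 points, and the rest of the gap to 80% comes from ranking itself.

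**6. A larger effect.** If the true effect is 0.63 SD, a logged outcome with a raw baseline has 92%, 90%, 96% and 92% power in the four settings, against 94%, 94%, 100% and 100% with both logged. The loss there is 2–8 points, and up to 9 on a repeat run.

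**7. Type I error.** It is 4.7–5.6% in every setting on the ρ 0.5 to 0.85 grid, with the transformation fixed in advance.

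**The case against.** The strongest reply is that the protocol never says baseline must stay raw. Section 11.3 asks only for an analysis that "will be assessed by ANCOVA model adjusting for baseline values", and a SAP not shown may set the covariate's scale. That is fair, and it is why the point concerns the sentence as written. Still, the sentence is not mere silence: it commits to a remedy and names only the outcome as its object.

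A second reply is that the remedy does help. With no transformation at all, power in the last three settings of the table is 53%, 52% and 38%, against 72%, 60% and 55% with only the outcome logged. This stands. The plan's remedy is an improvement that stops short.

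A third is that the losses depend on assumed skewness and correlation and on shrinking the effect as correlation rises. This also stands, and limits the size of the claim.

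A reader might go further and infer that most of the baseline adjustment is lost, or that power falls for all 45 markers. The documents do not support this. They give no skewness for any marker, mild skew costs little, and the remedy applies only where diagnostics fail. A reader might also infer that choosing the transformation after seeing residuals inflates false positives. That has not been shown: post hoc choice was not simulated, and section 14.3 gives the statistician a locked, blinded database. Blinding limits that worry, though it neither names a transformation nor makes effect scales comparable.

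**Conclusion.** The point holds in a limited form. Taken literally, the fallback in section 11.3 puts outcome and baseline on different scales, and for a strongly right-skewed marker this wastes precision. With the effect sized for about 80% power when both values are logged, the cost at 40 per arm is about 4 points at s = 0.6 and ρ = 0.6, about 20 points at 1.0 and 0.8, and about 25 points at 1.4 and 0.8. At an effect of 0.63 SD it is 2–9 points. These figures rest on assumed log-normal markers and on values of s and ρ that the protocol does not supply; 0.63 is itself borrowed from the symptom AUCs.

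Only secondary outcomes 5a to 5c are affected. The primary analyses are untouched, and there is no sign of type I error inflation when the transformation is fixed. It is a cheap improvement worth making, not a threat to the trial's main conclusions.

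**What to change.** In section 11.3, state that any transformation is applied to both the Day 84 and the baseline value. Make log of both the default for sIgA, IgA, IgG, IgE, IgM and the array markers, analysed by ANCOVA and reported as geometric mean ratios with 95% confidence intervals. Name ranks of both as the only fallback, and fix the choice for each marker on blinded pooled data before unblinding.

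The cost is wording in the protocol or SAP. Effects are then read as ratios, and a simple rule is needed for values below the detection limit. No extra data or participants are required.
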